5.8 Packaging

The study medications will be dispensed in sterile multi-dose eye droppers of 3 ml volume, which will be used as single-dose applications. One drop of the placebo/ drug solution will be administered to each eye. Therefore 4 eye droppers will be required per day. At each visit, subjects will receive 56 sterile multi-dose eye droppers that will be used as single-dose applications. The eye droppers will be placed in a dark (brown) colored packet before being dispensed to the subject. A label with abbreviated information will be placed on each eye dropper. The zip-lock packet will include the subject's name, stage of visit, instructions for drug use and storage and the drug expiration date. The label will also include the study name (abbreviated) and a statement that the drug is **investigational** for use only in

this research study." The first dose will be administered to the subject by the researcher from one of the eye droppers that will be dispensed to the subject at the first treatment visit (visit 2, day 1). No separate packing will be done for the study medication to be used in the MD's office. The subjects will receive the week's remaining doses in a dark packet with an ice pack to take home. Fifty-six sterile eye droppers will be dispensed at each visit.

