3.4 Safety Endpoints

Safety assessments include Vital Signs, recording of all complications and adverse events, as well as ophthalmic exam findings. All ocular and non-ocular adverse events will be assessed for severity and relationship to the investigational product.

Primary safety endpoint:

• The proportion of subjects at week 8 who were able to successfully complete a full eight weeks of therapy with topical administration four times per day (q.i.d.)

Secondary safety endpoint:

- All adverse events reported, whether deemed related to treatment, or not.
- Clinically significant changes in vital signs or ophthalmic examination from baseline.

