- 10. Do not reuse the dropper after use. Use another dropper for next dose.

The subject should repeat the above procedures for the other eye to demonstrate to the Investigator or designee that they are able to perform the drug administration satisfactorily. Subjects will be instructed to perform these steps on each administration of the study medication. Instructions for use will be included in the zip-lock packet with the study medication and site personnel will ensure that these instructions are given to the subject.

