5.9.3 Dispensing of Study Drug

At the first treatment visit (day 1), the first study medication dose will be administered to the subject in the clinic and eye droppers sufficient to last for 2 weeks will be given to them to take home. The subjects will be asked to return the used and unused eye droppers at the follow- up visits. We will then retrieve the previously -dispensed eye droppers and a fresh 2 week supply will be dispensed by the pharmacy. This will continue from week 2 to week 8. No new drug eye droppers will be given on the 6th (week 8) visit.

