6.5.3 Visit 3: Week 2 (± 2 days)

Treatment Visit (after any dose for that day)

- Vital Signs
- OSDI
- Clinical Global Impression, Subject Global Assessment
- Test Substance Tolerance (VAS)
- Ophthalmic Examination (slit lamp examination, Ocular surface redness score)
- Physical Inspection of the Nose and Oropharynx
- Review the subject's diary and record changes in concomitant medication, deviations from drug schedule and adverse events.
- Subjects will be given study medication, sufficient to last for 2 weeks, to take home.

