6.5.4 Visit 4: Week 4 (± 2 days)

Treatment Visit (after any dose for that day)

- Vital Signs
- OSDI
- Keratograph Oculus Redness Score
 - > Non-invasive Keratography Tear Film Break-up Time (NIKBUT)
 - > Tear Meniscus Height (TMH)
- TearLab Osmolarity Test
- InflammaDry Test for MMP-9 Protein
- Clinical Global Impression, Subject Global Assessment
- Test Substance Tolerance (VAS)
- Ophthalmic Examination (slit lamp examination, Ocular surface redness score)
- Physical Inspection of the Nose and Oropharynx
- Review the subject's diary and record changes in concomitant medication, deviations from drug schedule and adverse events.
- Subjects will be given study medication, sufficient to last for 2 weeks, to take home.

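### Each dispensing covers exactly 14 days and leftovers are taken back, but the visit windows allow intervals of 16 to 18 days

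*Combined protocol and SAP*

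**What the plan says.** Three sets of rules in the protocol bear on this.

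- **Supply.** Section 5.8 says "Therefore 4 eye droppers will be required per day" and "Fifty-six sterile eye droppers will be dispensed at each visit"; section 5.4 gives the same figures. Section 5.9.3 stops dispensing at week 8, so there are four dispensings: Day 1 and weeks 2, 4 and 6. The first clinic dose comes out of the same stock: "The first dose will be administered to the subject by the researcher from one of the eye droppers that will be dispensed to the subject". Section 5.4 rules out a second use of any dropper: "Do not reuse the dropper after use. Use another dropper for next dose".
- **Returns.** Section 5.9.3 says "We will then retrieve the previously -dispensed eye droppers and a fresh 2 week supply will be dispensed by the pharmacy". Section 5.5 also asks subjects to return unused droppers at every visit, as a compliance measure.
- **Windows.** Sections 6.5.3 to 6.5.6 allow two days either side of weeks 2, 4, 6 and 8.

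The primary safety endpoint in section 3.4 is "The proportion of subjects at week 8 who were able to successfully complete a full eight weeks of therapy" at four administrations per day. No missed-dose allowance is stated. Section 9.2.2 sets a 75% adherence level as the trigger for a discussion among investigators.

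**The concern.** A supply with no margin fits only if no interval between visits exceeds 14 days. The windows permit longer intervals, and the return rule stops an early visit from building a reserve for a late one. A subject who follows every instruction can therefore run out.

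Two things are at stake. First, the completion endpoint and the adherence measure are meant to reflect whether subjects can take the drops. Doses missed because no dropper was left would mix logistics into both. Second, a gap always falls at the end of an interval, immediately before the next assessment. For a late week 8 visit, that puts untreated days before the only post-baseline corneal staining, which is the primary efficacy measurement (section 3.2 and the schedule of visits), although section 3.1 calls that visit the last day of treatment.

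**Working it through.** **Inputs.** 56 droppers per dispensing and 4 per day (5.4, 5.8); four dispensings and retrieval of leftovers (5.9.3); windows of 2 days either way at weeks 2, 4, 6 and 8 (6.5.3 to 6.5.6). Visits are placed relative to the nominal date, in whole days after the first dose.

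**Step 1: reproduce the plan's figure.** 4 per day × 14 days = 56, as stated. Total supply is 4 × 56 = 224. Eight weeks need 56 days × 4 = 224. Overage is 224 − 224 = 0.

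**Step 2: longest compliant intervals.**

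- Day 1 to week 2: 14 + 2 = 16 days. Need 16 × 4 = 64; short by 64 − 56 = 8 doses (2 days).
- Any later interval, with one visit 2 days early and the next 2 days late (for example day 12, then day 30): 18 days. Need 18 × 4 = 72; short by 72 − 56 = 16 doses (4 days). Coverage of that interval is 56/72 = 77.8%.

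**Step 3: worst full course.** Visits at −2, +2, −2 and +2 days give intervals of 12, 18, 10 and 18 days, 58 in all. Doses possible are 48 + 56 + 40 + 56 = 200. Doses scheduled are 58 × 4 = 232. Coverage is 200/232 = 86.2%, with 32 doses missed.

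**Step 4: other readings.**

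- Dosing stops at day 56 (section 5.2 specifies 8 weeks): the same pattern gives 12, 18, 10 and 16 treated-or-due days, a shortfall of 4 + 2 = 6 days, or 24 of 224 doses.
- Windows counted from the previous visit: longest interval 16 days, 8 doses short.
- Leftovers kept by the subject: the worst interval shortfall drops to 8 doses but does not vanish. A week 8 visit at +2 days needs 232 doses against 224 dispensed, if dosing continues to that visit.
- Week 2 taken strictly as Day 14 (section 3.1 uses both labels): the first interval is at most 15 days, 60 − 56 = 4 doses short; later intervals are unchanged.

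Every reading leaves a shortfall for some compliant subject.

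**Step 5: how many visit patterns are affected.** There are 5⁴ = 625 whole-day patterns of the four visits. With leftovers retrieved, 610 contain at least one interval longer than 14 days. Only the pattern with every visit on its nominal day gives 224 doses with no gap. These are counts of patterns, not probabilities.

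**The case against.** The strongest reply is that this is a pharmacy matter with little effect on the results. Its parts carry different weight.

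- **Resupply may be possible.** Section 5.9.1 says in general terms that drug is dispensed to subjects on need. But sections 5.8 and 5.9.2 tie dispensing to visits, 5.8 fixes the count, and no resupply between visits is described. The general sentence does not remove the conflict.
- **Gaps may be uncommon or short.** This stands. A reader might infer from 610 of 625 patterns (97.6%) that nearly every subject would run out. That would require all five days of each window to be equally likely and visits to be independent. The documents instead plan two-weekly visits, with the window as a tolerance. The count also includes one-day gaps, and the 32-dose course is a single pattern that depends on dosing to day 58.
- **Subjects would not necessarily fail the endpoint.** This also stands. A reader might infer that a subject who runs out must be a non-completer. Section 3.4 does not say so, and the wording can be read as remaining on treatment.
- **Adherence stays acceptable.** Against scheduled doses, both the worst interval (77.8%) and the worst course (86.2%) remain above 75%. Supply gaps alone would not reach the trigger.
- **Reasons are already recorded.** Sections 3.1 and 5.5 have subjects note why a dose was missed, so supply gaps can be identified. What is absent is a rule for scoring them.
- **No bias between arms is shown.** Both masked arms share the same supply and windows, so gaps would be expected to be similar. A reader might infer a distorted treatment comparison; the documents give no basis for a direction or a size.

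**Conclusion.** The conflict is real and needs no assumption about how often visits run late: with retrieval of leftovers as written, any interval over 14 days exhausts the supply, and the windows allow such intervals. The size is at most 8 uncovered doses in the first interval and 16 in any later one, with total coverage no worse than about 86%. These figures assume that windows run from the nominal dates and that dosing continues to the week 8 visit; the other readings reduce the shortfall without removing it.

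The consequence for the completion endpoint is conditional. On a literal reading of section 3.4, a supply gap could be counted as non-completion; on a lenient one it would not. The documents do not settle which applies. They support neither a forecast of how many subjects would run out nor a claim that the efficacy comparison is biased. The point should be corrected because it touches the primary safety endpoint and the days before the primary efficacy measurement, and because the correction is simple.

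**What to change.** Reconcile the dispensed quantity, the visit windows and the return rule across sections 5.4, 5.5, 5.8, 5.9.3 and 6.5.3 to 6.5.6, so that either the supply covers the longest interval allowed or the windows match the supply. Make sections 3.1 and 5.2 agree on the last day of dosing when the week 8 visit is late.

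State in sections 3.4 and 9.2.2 that doses missed for lack of supply, identified from the diary reasons, are reported separately and not scored as subject failure in the completion endpoint or the adherence counts.

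**Cost.** Covering every interval in full takes up to 64 + 72 + 72 + 72 = 280 droppers per subject against 224, an increase of 56 (25%). For 72 subjects that is 56 × 72 = 4,032 droppers, or 2,016 ampules at two droppers each (section 5.4). The shelf life of the repackaged, preservative-free droppers is not stated and would have to allow 18 days. Tightening the windows needs no extra droppers but leaves less scheduling freedom. The scoring rule needs only wording. No change to the regimen is proposed.

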5.9 Receiving, Storage, Dispensing and Return

5.9.1 Receipt of Drug Supplies

The UIC Investigational Drug Service (IDS) will order the study drug. The study drug will be stored in the Taylor Street/ EEI pharmacy and dispensed to subjects as needed.

5.9.2 Storage

Study medication will be stored at EEI pharmacy until such time as a subject visit is scheduled. The study medication will be directly dispensed to the subject from the EEI pharmacy on each treatment visit, except for the first dose that is administered in the clinic under the supervision of research personnel. The study medication will not be stored in the MD's office, except when a subject receives his/her first dose, when the medication may be kept in the MD's office for a maximum of 2- 3 hrs in the ice pack provided by the EEI pharmacy.

5.9.3 Dispensing of Study Drug

At the first treatment visit (day 1), the first study medication dose will be administered to the subject in the clinic and eye droppers sufficient to last for 2 weeks will be given to them to take home. The subjects will be asked to return the used and unused eye droppers at the follow- up visits. We will then retrieve the previously -dispensed eye droppers and a fresh 2 week supply will be dispensed by the pharmacy. This will continue from week 2 to week 8. No new drug eye droppers will be given on the 6th (week 8) visit.

5.9.4 Return or Destruction of Study Drug

At the completion of the study, there will be a final reconciliation of drug ordered/ received, drug consumed, and drug remaining. Any discrepancies will be investigated, resolved, and documented. The used drug eye droppers will finally be disposed by the pharmacy according to the pharmacy standard protocols.

6 Study Procedures

6.1 Subject Recruitment and Screening

Prior to recruitment of any subjects into the study, written approval of the protocol and informed consent will be obtained from the Institutional Review Board (IRB).

Potential subjects will be recruited from the clinical practice of the investigator at the time of their routine eye examination visit. The clinical practice is located at the Department of Ophthalmology and Visual Sciences, Eye and Ear Infirmary, [name]. Patients with oGVHD will be approached by a member of the research staff to determine if the subject might be interested in participating in a research study. If the subject is interested, the research staff member will describe the study. If the subject is willing to enter the study, the subject will be asked to review the

study consent form, the PI will meet with the subject to review the form, the study will be discussed to conform the subject's understanding of the study, and to answer any questions that the subject might have. Once the subject demonstrates understanding of the study and agrees to participate in the study, the subject will be asked to sign the informed consent form in the presence of the PI. Patients that contact the researchers in response to a flyer and information sheet provided by their physician will be scheduled for a visit to discuss the study and participate in the consent process. Consent will be obtained prior to screening to determine eligibility. Subjects will be screened for eligibility, as per the inclusion/ exclusion criteria, and as detailed in section 6.5.1. Eligible subjects will be enrolled in the study.

6.2 Assignment of Subject Identification

A study identification (ID) number will be assigned to each subject at screening. This study ID number will be used on all study-related documents. To maintain confidentiality, the subject's name will not be recorded on any study document other than the informed consent form. The master code list will link the subject MRN to the study ID number given to each subject. The master code list will be stored on the desktop in PI's OFFICE in Lions of Illinois Eye Research Institute (LIERI). The data collected and master code list will be accessible only to the PI and the research team involved in this project. The desktops will be password protected as well. Data will not be shared over the internet and will remain password protected. Confidentiality will be maintained. Data will be de-identified once study is completed and for subjects determined to not meet eligibility criteria or who later decline participation in the consent process.

6.3 Screen Failure

A record of screen failures and the reasons for non-eligibility to the study will be maintained.

6.4 Subject Enrollment

Subjects meeting the enrollment criteria (see Sections 4.1 and 4.2) will be eligible for the study.

6.5 Study Assessments

The following detailed procedures are performed at the designated clinic visit. All results will be documented on the subject's medical/research charts, source documents, and CRFs as required. All ophthalmic procedures will be performed on both eyes.

6.5.1 Visit 1 Screening Day -18 to 0

After obtaining informed consent, the following assessments will be performed within fourteen days prior to the subject receiving the first dose of study medication:

- Demographic information including: birth date, gender, race or ethnic origin.
- Medical History including prior medication use and prior procedures: Medical history will be
 obtained by interviewing the subject and will include a history of systemic (acute or chronic)
 GVHD, stem cell transplant history (including the date and type of transplant, degree of
 mismatch, if any, etc.), allergic history (including medications and food), substance abuse history

RhDNase treatment for ocular GVHD Version: 10.0; 07-26-2018

Page 29 of 47

(including alcohol) and a history of medication use (including prescription, OTC, and herbal products) during the past 30 days will also be completed.

- Ophthalmic history including: date when the oGVHD began, verification that the subject has had definite oGVHD, medications used by the subject to treat oGVHD, previous procedures to treat oGVHD. Ocular symptoms due to oGVHD will be quantified using the Ocular Surface Disease Index (OSDI) questionnaire (section 3.3.2).
- Ophthalmic Examination (slit lamp examination, Ocular Surface Redness Score, Fluorescein and Lissamine Dye staining, and a Schirmer 1 test)
- Pregnancy test (urine), if applicable. Women of reproductive age will be asked to use a method
 of birth control that is acceptable to the subject and the study doctor. This may include oral
 contraceptive pills, birth control implants/shots or patches, barrier methods or abstinence.
 Women of reproductive age will not be included in the study if they refuse to use any birth
 control measure, including abstinence.

Subjects currently treating oGVHD with corticosteroids and/or Restasis will continue these treatments during the whole study. If patients are wearing contact lenses (Soft bandage contact lenses or PROSE lens), they will be asked to discontinue contact lens wear for 1 month prior to being enrolled (Baseline visit) and will be required to not wear contact lenses for the duration of the study (until week 10 visit). The study doctor will provide advice about decreasing oGVHD symptoms with artificial tears, eyelid massage, or warm compresses.

If the subject agrees to enter the study, the first treatment visit will be scheduled. If a washout period is needed, visit 2 will be after 2 weeks (±4 days). If a washout period is not necessary, visit 2 can be scheduled any time in the next 2 weeks after the screening visit.

6.5.2 Visit 2 Day 1 (Randomization and First treatment visit) Prior to first dose (Baseline)

- Vital Signs (blood pressure taken while subject is relaxed in a sitting position for at least 3 minutes, pulse, temperature, and height and weight (at this visit only).
- BSCVA (Snellen's chart)
- OSDI
- Schirmer 1 test and Fluorescein and Lissamine Dye staining
- Keratograph Oculus Redness Score
 - > Non-invasive Keratography Tear Film Break-up Time (NIKBUT)
 - > Tear Meniscus Height (TMH)
- TearLab Osmolarity Test
- InflammaDry Test for MMP-9 Protein
- Baseline Ophthalmic Examination (slit lamp examination, Ocular surface redness score)
- Tear fluid collection for analysis (PicoGreen, Cellometry)
- Physical Inspection of the Nose and Oropharynx
- Conjunctival and eyelid margin cultures
- Record changes in concomitant medication
- Adverse events since screening visit.

Randomization (by pharmacy)

Investigator/designee administers first dose

Post-Dose

RhDNase treatment for ocular GVHD Version: 10.0; 07-26-2018

Page 30 of 47

- Test Substance Tolerance (Visual Analogue Scale; VAS)
- Subjects will be trained on how to self-administer the study eye drops and be given a sufficient supply to last for 2 weeks to take home.
- Subjects will receive a study diary on which to record the day/time of each dose and any adverse effects.
- Post dose evaluation for any adverse effects.

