Contact lenses, commonly used to treat oGVHD, will be withheld during the course of this study. This is necessary as the proposed primary efficacy outcome measure is corneal Fluorescein and Lissamine Dye Staining. Contact lenses can directly reduce corneal SPK and staining due to ensconcing and acting like a bandage that prevents corneal exposure to tear fluid inflammatory materials. Thus, because of over lapping effects on the primary outcome measure, it may not be possible to attribute any observed clinical benefit to rhDNase I treatment if contact lenses are used concurrently. This approach has been used in other clinical trials that have investigated the use of an anti-inflammatory agent in dry eye disease (NIH funded 'Dry Eye Evaluation and Management (DREAM) study').⁴¹

Stopping contact lens wear may increase the risk of worsening of oGVHD during the wash-out period and during the course of the study. However, because other eye drop treatments will continue during

the wash out period as well as during the course of the study, we do not expect any significant clinical worsening during the study. We do however expect the frequency of use of artificial tears to go up during the wash out period and during the course of the study.

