7.1 Sample Size Determination

The sample size is based on the primary efficacy end point (corneal RBS score) using the following assumptions: (i) mean RBS score in ocular GVHD population = 3.1, (ii) sigma (standard deviation) = 2.5, (iii) expected mean based on 60% effect = 1.24. These assumptions are based on our preliminary data in ocular GVHD patients where we found that treatment with DNase I eye drops reduced RBS score by 80% (mean).²⁵ A total of 30 subjects in each group will be required to detect the difference between groups using a 2-sided two-sample t test with an alpha level of 0.05 and 80% power. We elected to enroll 36 subjects per group.

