7.2 Statistical Methods

Biostatisticians from the Design and Analysis Core (DAC) of UIC-CCTS will perform the analysis. We will assess treatment efficacy based on the intent-to-treat principle using each participant's randomized treatment assignment to define treatment groups and outcomes. Safety variables will be analyzed with regard to treatment that participants actually received (the safety population). One eye (target eye) will be selected at screening visit for statistical comparisons as follows: (i) if only 1 eye meets inclusion criteria, this eye is used; (ii) if both eyes meet inclusion criteria, the eye with the higher RBS score is used; (iii) if both eyes have the same RBS score, then the one with the lower Schirmer I score is used; (iv) if both eyes have same scores, the right eye is used. Secondary analyses will be performed for the non-target eye as well. To assess the effect of treatment, we will compare each outcome measure between rhDNase I (study) vs. Vehicle (control) group over time using general linear mixed model, mixed-effects ordinal logistic regression, and mixed-effects multinomial logistic regression for continuous, ordinal and nominal variables respectively. Treatment, time and their interaction will be included in the model. Missing values of less than 25% will be imputed by using multiple imputations; otherwise will not be included in the analysis. Descriptive statistics will be utilized before the modeling to describe the sample. Assumptions behind each statistical method will be examined. Two-sided Pvalue less than 0.05 would be considered as statistical significance. All the analyses will be conducted by using SAS 9.2 (SAS Inst., Cary, NC).

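### Corneal staining is graded twice before treatment, but the section 7.2 model names neither score as a covariate and so gives up precision on the primary endpoint

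*Combined protocol and SAP*

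**What the plan says.** **Measurements.** Section 6.5.1 lists at screening: "Ophthalmic Examination (slit lamp examination, Ocular Surface Redness Score, Fluorescein and Lissamine Dye staining, and a Schirmer 1 test". Section 6.5.2 repeats the staining on Day 1 before the first dose. Section 6.5.6 and the Schedule of Visits place the only later grading at week 8. The primary efficacy endpoint (section 3.2) is the reduction in corneal staining after 8 weeks.

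**Analysis.** Section 7.2 compares the arms over time with a mixed model: "Treatment, time and their interaction will be included in the model". It does not say whether the Day 1 score is an outcome level, is constrained equal between arms, or is a covariate. The screening visit is used to choose the target eye (by a rule worded in RBS score) and has no role in the model. Section 5.3 allocates by 72 unrestricted draws, without blocking or stratification.

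**Contact lenses.** Section 5.6 says lenses can directly lower corneal staining, and "Stopping contact lens wear may increase the risk of worsening of oGVHD during the wash-out period and during the course of the study". Section 6.5.1 adds: "If a washout period is needed, visit 2 will be after 2 weeks (±4 days". The washout is 14 days in section 1.5, one month before baseline in sections 4.2, 5.6 and 6.5.1, and about two weeks between visits in section 6.5.1.

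**The concern.** With a single post-treatment staining grade, pre-treatment scores are the main source of extra precision on the primary endpoint. Two are collected and neither is named as a covariate.

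For this endpoint, a time factor exists only if a pre-treatment visit is one of its levels. If Day 1 is that level and the arms' Day 1 means are left free, the interaction contrast is the difference in mean change. That removes Day 1 differences in full, which is inefficient when the correlation between visits is moderate or low. If only the week 8 score is compared, no baseline information is used.

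With 72 subjects and unrestricted allocation, chance differences in starting severity are to be expected. Covariate adjustment reduces their influence on the estimate at little cost. Former lens wear is a second candidate, because the protocol itself links lenses to staining.

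**Working it through.** **1. Reproduce the plan's figure.** Section 7.1 gives "mean RBS score in ocular GVHD population = 3.1", "expected mean based on 60% effect = 1.24" and "sigma (standard deviation) = 2.5", so the difference is 3.1 − 1.24 = 1.86. The test is specified as "using a 2-sided two-sample t test with an alpha level of 0.05 and 80% power".

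- Normal approximation: n = 2 × (1.960 + 0.842)² × 2.5² / 1.86² = 28.4, so 29 per arm.
- Exact noncentral t: 30 per arm, power 80.9%. The stated 30 reproduces.
- At the planned 36 per arm: 88.4% (normal), 87.6% (t).

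This calculation takes no credit for any baseline score.

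**2. Variance factors.** Let r be the correlation between staining scores at any two visits, taken equal for all pairs. The documents do not give r; I assume 0.3, 0.5 and 0.7. The variance of the treatment contrast, relative to the week 8 score alone, is:

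- change from Day 1: 2(1 − r)
- ANCOVA on Day 1: 1 − r²
- ANCOVA on Day 1 and screening: 1 − 2r²/(1 + r)

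Power at 36 per arm uses SE = 2.5 × √(factor × 2/36) and the normal approximation:

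| Analysis | Factor, r = 0.3 / 0.5 / 0.7 | Power, r = 0.3 / 0.5 / 0.7 |
|---|---|---|
| Week 8 score only | 1 / 1 / 1 | 88.4 / 88.4 / 88.4% |
| Change from Day 1 | 1.40 / 1.00 / 0.60 | 76.0 / 88.4 / 98.3% |
| ANCOVA, Day 1 | 0.91 / 0.75 / 0.51 | 91.1 / 95.4 / 99.3% |
| ANCOVA, Day 1 + screening | 0.862 / 0.667 / 0.424 | 92.5 / 97.2 / 99.8% |

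The 1.86 and 2.5 are Rose Bengal figures, whereas section 3.3.1 grades corneal fluorescein in five zones of 0–3. The variance ratios do not depend on the scale. The power figures do, and are illustrative.

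**3. Where the gain arises.** Against the change contrast, Day 1 adjustment multiplies variance by (1 + r)/2, a cut of 35 / 25 / 15%. The screening score then cuts the remaining variance by r²/(1 + r)²:

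- r = 0.3: 0.09/1.69 = 5%, worth 72 × (1/0.947 − 1) ≈ 4 subjects
- r = 0.5: 0.25/2.25 = 11%, about 9 subjects
- r = 0.7: 0.49/2.89 = 17%, about 15 subjects

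In power, Day 1 adjustment adds 15.1 / 7.0 / 1.0 points over the change contrast, and the screening score adds a further 1.4 / 1.8 / 0.5. At r = 0.7, measured against the change contrast, the two steps remove similar amounts of variance (0.60 to 0.51, then to 0.424). In the other comparisons Day 1 accounts for most of the gain.

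**4. If correlation decays with time.** Let a be the Day 1–week 8 correlation, b screening–week 8 and c screening–Day 1. The further cut is (b − ac)² / [(1 − c²)(1 − a²)]. Assumed values:

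- a = 0.60, b = 0.55, c = 0.7: 0.13² / (0.51 × 0.64) = 5.2%
- a = 0.60, b = 0.55, c = 0.8: 0.07² / (0.36 × 0.64) = 2.1%
- a = 0.60, b = 0.54, c = 0.8: 0.06² / (0.36 × 0.64) = 1.6%

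The range is about 1.5–5%.

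**5. Cost.** One degree of freedom out of about 70 costs roughly 1/70 = 1.4% of variance. At the low end of step 4 this nearly cancels the gain from the screening score.

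**6. Lens status, illustration only.** In a simulation of 72 subjects with r = 0.5, I assumed 20% lens wearers, a screening score lowered by 2 points in wearers, and a week 8 shift of 1 point. The SE of the treatment effect was 0.518 with Day 1 alone, 0.512 adding lens status, 0.507 adding the screening score, and 0.485 adding both. None of these lens inputs is in the documents.

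**The case against.** The strongest reply is that the planned analysis is valid, the stated 30 per arm reproduces, and 36 per arm leaves a margin. If Day 1 is a time level, the interaction already compares change from Day 1, so protection against baseline imbalance is not absent. The screening score is also an imperfect second baseline: the target eye is chosen at that visit, and in lens wearers it may be taken before or early in washout. Equal correlation is therefore optimistic, and the gain could be as low as 1.5%. All of this stands. It limits the size of the point, and it is why the two scores should be entered separately and not averaged. It does not explain leaving Day 1 adjustment unspecified.

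Two stronger readings are tempting, and the documents support neither.

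- *Uneven numbers of former lens wearers would bias the result.* A reader might multiply an unlucky between-arm difference by an assumed worsening in wearers and set the product against 1.86. Under randomisation the expected difference is zero, and chance imbalance is sampling variation carried by the standard error. The documents give neither the share of wearers nor the size of any worsening after Day 1. Section 5.6 goes on to say that no significant clinical worsening is expected. The 1.86 is also on the Rose Bengal scale, not that of the endpoint.
- *Lens status is already in the data.* Staff must know it to schedule visit 2, but it is not a listed screening item in section 6.5.1. Visit timing cannot stand in for it, since subjects without washout may also return at any time within the two weeks.

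**Conclusion.** The point holds as a loss of efficiency. Section 7.2 forgoes precision available from two pre-treatment staining scores that the trial already collects. There is no bias and no inflation of type I error.

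Under assumed equal correlations of 0.3–0.7, Day 1 adjustment cuts variance by 15–35% relative to an unconstrained change contrast, or by 9–49% relative to the week 8 score alone. The screening score adds a further 5–17%, or about 1.5–5% if correlation decays, before the cost of about 1.4% per covariate. Day 1 adjustment is therefore the essential part, and the screening score is a modest addition whose net value could be close to zero. The benefit of a lens term cannot be sized from the documents. All magnitudes rest on correlations that the protocol does not state.

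**What to change.** In section 7.2, pre-specify for week 8 corneal fluorescein staining in the target eye an ANCOVA, or an equivalent mixed model with Day 1 means constrained equal between arms. Enter the Day 1 pre-dose score and the target eye's screening corneal fluorescein score as separate covariates, not averaged.

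Optionally, add contact-lens discontinuation before Day 1 (yes/no). This needs a field on the case report form, and the washout passages in sections 1.5, 4.2, 5.6 and 6.5.1 must first be reconciled so that the term has one meaning.

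Cost: one or two sentences in section 7.2 and no new staining measurements. Each covariate uses one degree of freedom out of about 70. The lens term would add one recorded item per subject. The sample size need not change.
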